7 CLINICAL STUDY ASSESSMENT

7.1 Efficacy Assessments

7.1.1 [REDACTED] Photographic Scale of Glabellar Line Severity

7.1.2 Static [REDACTED] Categorical Scale

Effective date: 2018-08-10 13:08

Effective

Version: 1.0

The image consists of a grid of horizontal bars. The bars are primarily black, with a few white bars interspersed. One bar in the center contains a white grid pattern. The bars are arranged in a staggered, non-uniform grid. The white bar with the grid pattern is located in the middle row, with black bars above and below it. The black bars are of varying lengths and positions, creating a sense of depth and non-linearity. The overall effect is abstract and minimalist.

7.2 Safety Assessment

A safety assessment will be conducted for all subjects at the screening visit (from the informed consent signature) and at subsequent visits as outlined in the Schedule of Assessments (Table 2). Safety parameters include an evaluation of safety data by DSMC, TEAEs, laboratory testing (chemistry and hematology), focused physical examination findings, vital signs, and neutralizing antibody production.

7.2.1 Data Safety Monitoring Committee (DSMC)

The un-blinded independent DSMC will be appointed by the Sponsor to include a minimum of three physicians with pertinent botulinum toxin expertise and a biostatistician.

The committee will review safety data after subjects [REDACTED] complete the Month 1 follow-up visit.

Evaluation of safety data will include [REDACTED] the following stopping criteria:

The study will discontinue enrollment if evaluation of the safety data by the DSMC meets the stopping criteria, as outlined above. Further, the DSMC will review the list of AEs (including confirmed AEs of local or remote spread of toxin) and advise the Sponsor of safety finding that may result in discontinuation of study enrollment.

[REDACTED]

[REDACTED]

7.2.2 Focused Physical Examination

Investigator or designee will perform a physical examination of the subject that includes the face, head, and neck. Further details are provided in Appendix 4.

[REDACTED]

The Investigator may choose to investigate any other sign that he/she observes during the physical examination and should assess all abnormal findings for clinical significance.

Clinically significant abnormal findings at the screening visit and baseline visits are exclusionary, and the subject should not be enrolled in the study. If the abnormality is not clinically significant, capture it as medical history.

For any clinically significant changes from the baseline visit, an AE is to be recorded.

7.2.3 Vital Signs

Vital signs will be evaluated at the baseline visit (pre and post-treatment), and at each study visit

[REDACTED]

Vital signs will include blood pressure, heart rate, and respiratory rate. The subject should be in a seated position and resting for at least 10 minutes prior to taking vital sign measurements. Vital signs are to be taken prior to any blood draw, excluding baseline post-treatment measurements.

All abnormal values at the screening visit identified as clinically significant by the Investigator, will be recorded in the medical history.

For any clinically significant changes from the screening visit, an AE is to be recorded.

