7.2.4 Laboratory Safety Tests

The following laboratory safety tests shall be performed

[REDACTED]

- Hematology: White blood cell (WBC) count with differential, red blood cell (RBC) count, haemoglobin (Hb), hematocrit (hct), and platelet count (Plt)
- Blood chemistry: Creatinine, urea nitrogen, gamma glutamyl transferase (GGT), alkaline phosphatase (ALP), aspartate aminotransferase (AST=SGOT), alanine aminotransferase (ALT=SGPT), and bilirubin (total and conjugated)

The Investigator or a medically qualified sub-Investigator must review and evaluate laboratory values for each subject in a timely manner. The Investigator or designee will initial and date all laboratory reports and note directly on the report whether or not each out of range laboratory value is clinically significant. An out of range laboratory value should be considered as clinically significant if either of the following conditions is met:

- The abnormality suggests a disease and/or organ toxicity.
- The abnormality is of a degree that requires additional active management, e.g. close observation, more frequent follow-up assessments, or further diagnostic investigation.

For each out of range laboratory result, the Investigator or designee will assess for clinical significance.

All clinically significant out-of-range laboratory values for blood samples collected at baseline will be recorded in the medical history. All clinically significant out of range laboratory values for blood samples collected after baseline are to be reported as an AE if this abnormality was not present at the baseline visit or is assessed as having worsened since the baseline visit (i.e., there is a significant change from baseline). In instances when a laboratory abnormality is reported, the Investigator is to provide a diagnosis rather than reporting individual laboratory abnormalities, whenever possible. See Section 7.2.6.1.1 for additional details.

A summary of sample volumes and the number of blood samples will be included in a Laboratory Manual.

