7.2.6.1 Definitions

7.2.6.1.1 *Adverse Events (AE)*

According to ICH E2A, an AE is any untoward medical occurrence in a patient or a clinical investigation subject administered a pharmaceutical product and which does not necessarily have a causal relationship with this treatment. An AE can therefore be any unfavorable and unintended sign (including an abnormal laboratory finding), symptom, or disease temporally associated with the use of a medicinal (investigational) product, whether or not related to the medicinal (investigational) product.

Thus any new sign, symptom or disease, or any clinically significant worsening of an existing sign, symptom or disease (including new episodes of a chronic disease [e.g., hay fever, allergy]) compared to the condition at the first visit, should be considered as an AE. Lack of efficacy is not considered as an AE.

Notes:

- There should be an attempt to report a diagnosis rather than the signs, symptoms or abnormal laboratory values associated with the report of an AE. However, a diagnosis should be reported only if, in the investigator's judgment, it is relatively certain. Otherwise, symptoms, signs, or laboratory values should be used to describe the AE.
- Pregnancy is not to be considered as an AE; however, is an important medical event that must be monitored as described in Section 7.2.6.2.3.

7.2.6.1.2 *Treatment Emergent Adverse Event (TEAE)*

A TEAE is an event that emerges during treatment, having been absent pre-treatment, or worsens relative to the pretreatment state.

Investigators are responsible for monitoring, recording, and reporting all AEs that occur during the study as described. TEAEs will be delineated from AEs following database lock.

7.2.6.1.3 *Serious Adverse Events (SAE)*

A SAE is any untoward medical occurrence that at any dose:

- Results in death,
- Is life-threatening,
- Requires inpatient hospitalization or prolongation of existing hospitalization,

- Results in persistent or significant disability/incapacity, or
- Is a congenital anomaly/birth defect.

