9.1.3.1 Safety Analysis

A summary of all AEs will be provided, which will include:

- number of subjects who did not have an AE
- number of subjects with at least one AE and number of events
- number of subjects with at least one TEAE and number of events
- number of subjects with at least one related TEAE and number of events
- number of subjects with at least one TEAE by causality
- number of subjects with at least one TEAE by maximum intensity
- number of subjects with at least one TEAE leading to discontinuation
- number of subjects with at least one serious TEAE.

All TEAEs, treatment emergent SAEs, TEAEs by maximum intensity, TEAEs by causality, TEAEs by maximum intensity and causality, and TEAEs leading to discontinuation will be summarized by SOC and PT including number of subjects with at least one event, percentages, and number of events. All related TEAEs will also be summarized by time to onset and duration.

Data for hematology, blood chemistry, antibodies, and vital signs will be summarized by descriptive statistics with the value at each visit as well as the change from baseline. Shift tables for out of normal ranges results will be presented for hematology, blood chemistry and antibodies. The numbers and percentages of subjects with abnormalities in physical examination and vital signs will also be summarized. The results of the urine pregnancy tests will be listed.

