## 1.3 Efficacy Assessments

For all assessments, baseline will be defined as the observation that is closest to but prior to study treatment on Day 0. Likewise, change from baseline will be calculated as the value at a given time point minus the baseline value.

- [REDACTED]
- [REDACTED]
- [REDACTED]
- [REDACTED]

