### 2.5.3 Other Safety Assessments

Data for hematology, blood chemistry, [REDACTED] and vital signs will be summarized by treatment group using descriptive statistics with the value at each visit as well as the change from baseline. The numbers and percentages of subjects with abnormalities in focused physical examination will also be summarized by treatment group. The results of the urine pregnancy tests will only be listed.

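### The vital-sign AE rule compares post-injection readings with screening, not with the pre-treatment Day 0 reading, so AE counts can miss a change that the vital-sign tables show

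*Protocol*

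**What the plan says.** Protocol 7.2.3 sets the recording rule for vital signs: "For any clinically significant changes from the screening visit, an AE is to be recorded". SAP 1.6(v) repeats it word for word. Clinically significant abnormal values at screening go to medical history.

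The same protocol section provides a pre-dose reading on the day of injection: "Vital signs will be evaluated at the baseline visit (pre and post-treatment), and at each study visit".

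The two neighbouring safety rules use a different reference:
- Physical examination (Protocol 7.2.2): "For any clinically significant changes from the baseline visit, an AE is to be recorded".
- Laboratory tests (Protocol 7.2.4): a clinically significant out-of-range value is an AE "if this abnormality was not present at the baseline visit or is assessed as having worsened since the baseline visit".

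The tables also use baseline. Protocol 9.1.3.1 says "vital signs will be summarized by descriptive statistics with the value at each visit as well as the change from baseline", and SAP 2.5.3 says "vital signs will be summarized by treatment group using descriptive statistics with the value at each visit as well as the change from baseline". SAP 1.6(v), which carries the screening rule, itself lists change from baseline as a vital-sign endpoint. SAP 1.3 states that "baseline will be defined as the observation that is closest to but prior to study treatment on Day 0". That sentence is worded to cover all assessments but sits under the efficacy heading.

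Two definitions in Protocol 7.2.6.1 bear on this. The general AE definition compares with the subject's state at the first visit. The TEAE definition covers an event "having been absent pre-treatment, or worsens relative to the pretreatment state".

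**The concern.** The question a post-injection vital sign should answer is whether it changed after the injection. The protocol collects the reading needed for this, taken shortly before treatment, but the AE rule points to a different visit. Vital signs are the exception among the three rules, and the AE record and the vital-sign tables then measure change from different starting points.

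What is at stake is the AE and TEAE counts. The protocol separates TEAEs out of the recorded AEs after the database is locked, so an AE that a site never entered cannot be recovered at that stage. Protocol 9.1.3.1 also plans counts of subjects with vital-sign abnormalities, but SAP 2.5.3 as published keeps such a count for the physical examination only, and SAP 2.1 lets the SAP supersede the protocol's statistical sections. In the published SAP text, the AE tables are therefore where a clinically important vital-sign change becomes a number of subjects per treatment group.

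**Working it through.** The plan gives no figure to reproduce. The check compares the reference point in each rule, then uses assumed readings to test whether a change can escape the AE rule.

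**Reference points**

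| Item | Place | Reference |
|---|---|---|
| Vital-sign AE | Protocol 7.2.3; SAP 1.6(v) | Screening visit |
| Physical-examination AE | Protocol 7.2.2 | Baseline visit |
| Laboratory AE | Protocol 7.2.4 | Baseline visit |
| Vital-sign tables | Protocol 9.1.3.1; SAP 2.5.3 | Baseline |
| AE in general | Protocol 7.2.6.1.1 | First visit |
| TEAE | Protocol 7.2.6.1.2 | Pre-treatment state |
| TEAE classification | SAP 1.6(i) | Onset at or after dosing |

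**Relation between the two changes**

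Change from screening = change from pre-dose + (pre-dose − screening).

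The two agree only if the pre-dose value equals the screening value. If the pre-dose value is lower, a rise after injection looks smaller from screening by exactly that gap.

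**Assumed readings, inside the alert limits**

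The eCRF alert ranges in SAP Table 4 are 90-150 mmHg for systolic pressure and 50-100 beats/min for heart rate. They are absolute limits and do not test change from any visit.

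| Measure | Screening | Pre-dose | Post-dose | From pre-dose | From screening |
|---|---|---|---|---|---|
| Systolic (mmHg) | 148 | 118 | 148 | 148 − 118 = +30 | 148 − 148 = 0 |
| Heart rate (beats/min) | 98 | 70 | 98 | 98 − 70 = +28 | 98 − 98 = 0 |

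Every value is in range, so no alert fires. The change from screening is zero, so the rule does not call for an AE. The change-from-baseline tables would include +30 and +28.

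**Assumed readings, outside the alert limits**

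Systolic 165 at screening, 130 pre-dose and 168 post-dose gives +38 from pre-dose and +3 from screening. Here 168 exceeds 150, so the eCRF prompts an assessment of clinical significance. The stated AE comparison is still with screening.

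**Reverse case**

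Systolic 118 at screening, 148 pre-dose and 148 post-dose gives 0 from pre-dose and +30 from screening. The rule can call for an AE, but the shift was already present before dosing. With its onset dated correctly, SAP 1.6(i) does not count it as a TEAE. It becomes one only if the onset is dated to the post-dose reading.

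**The case against.** The strongest defence is that the screening reference may be deliberate. AE collection starts at consent, and the general AE definition compares with the first visit, so the vital-sign rule follows that definition. It also pairs with the medical-history rule: significant screening findings are history, and later changes are events. This stands as a reason to keep screening for findings before injection, and it means that changing Protocol 7.2.3 alone would create a new mismatch with 7.2.6.1.1. It does not explain why post-injection readings should bypass a pre-dose value taken on the same day, or why the other two rules use baseline.

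Second, the rule requires an AE in one situation and does not forbid one in others. The general definition is broad enough for an investigator to record a post-injection change anyway, and clinical significance is a judgement. Nothing shows that an investigator would call a rise from 118 to 148 significant. This stands, and it limits the point to what the rule can fail to call for.

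Third, a reader might infer that missed changes disappear from the dose comparison and from safety oversight. The documents do not support that. SAP 2.5.3 summarizes change from baseline by treatment group, SAP 2.1.2 adds quartiles, minimum and maximum and lists all eCRF data, and SAP 2.6.1 has the DSMC work from summary tables and listings. Only the AE and TEAE counts are exposed.

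Fourth, the Day 0 definition sits under an efficacy heading, so applying it to vital signs is a reasonable inference rather than explicit text. Part of Protocol 7.2.3 is also redacted, but the AE sentence is complete and appears in both documents.

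**Conclusion.** The inconsistency is real and minor. For post-injection readings, the stated rule uses a reference that differs from the neighbouring safety rules, the vital-sign tables and the TEAE concept. Followed literally, it can leave a change out of the AE and TEAE counts while the summaries and listings still show it. The conclusion rests on a literal reading of the rule and on applying the Day 0 baseline definition to vital signs. The example readings are assumed.

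Two stronger readings are tempting and unsupported. One is that misclassification is shown in both directions; the reverse direction needs a misdated onset.

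The other is a rate. If one assumes a within-subject systolic SD of 10 mmHg (range 6-14), the difference between two visits has SD √2 × 10 = 14.1 (8.5-19.8), and about 29% (8-45%) of differences exceed 15 mmHg in either direction. This is visit-to-visit noise, not a missed-AE rate. Neither the SD nor the cut-off is in the documents, and under the same assumption the same share applies to any follow-up visit compared with Day 0. Because the documents give neither vital-sign variability nor a numeric threshold for clinical significance, the frequency cannot be computed.

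**What to change.** 1. In Protocol 7.2.3 and SAP 1.6(v), keep screening as the reference for findings before injection. For every post-injection reading, including the Day 0 post-treatment one, make the reference the pre-treatment Day 0 measurement.
2. Reconcile the first-visit comparison in Protocol 7.2.6.1.1 at the same time, so that the general AE definition and the vital-sign rule agree.
3. State in the SAP that the baseline definition in 1.3 applies to vital signs.
4. Carry the same reference into the eCRF guidance.

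The cost is about one sentence in each place and no new measurement. The downside is that a few more vital-sign changes go to the investigator for a significance judgement.

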7.2.4 Laboratory Safety Tests

The following laboratory safety tests shall be performed

[REDACTED]

- Hematology: White blood cell (WBC) count with differential, red blood cell (RBC) count, haemoglobin (Hb), hematocrit (hct), and platelet count (Plt)
- Blood chemistry: Creatinine, urea nitrogen, gamma glutamyl transferase (GGT), alkaline phosphatase (ALP), aspartate aminotransferase (AST=SGOT), alanine aminotransferase (ALT=SGPT), and bilirubin (total and conjugated)

The Investigator or a medically qualified sub-Investigator must review and evaluate laboratory values for each subject in a timely manner. The Investigator or designee will initial and date all laboratory reports and note directly on the report whether or not each out of range laboratory value is clinically significant. An out of range laboratory value should be considered as clinically significant if either of the following conditions is met:

- The abnormality suggests a disease and/or organ toxicity.
- The abnormality is of a degree that requires additional active management, e.g. close observation, more frequent follow-up assessments, or further diagnostic investigation.

For each out of range laboratory result, the Investigator or designee will assess for clinical significance.

All clinically significant out-of-range laboratory values for blood samples collected at baseline will be recorded in the medical history. All clinically significant out of range laboratory values for blood samples collected after baseline are to be reported as an AE if this abnormality was not present at the baseline visit or is assessed as having worsened since the baseline visit (i.e., there is a significant change from baseline). In instances when a laboratory abnormality is reported, the Investigator is to provide a diagnosis rather than reporting individual laboratory abnormalities, whenever possible. See Section 7.2.6.1.1 for additional details.

A summary of sample volumes and the number of blood samples will be included in a Laboratory Manual.

7.2.5 Neutralizing Antibody Testing

[REDACTED]

[REDACTED]

[REDACTED]

7.2.6 Adverse Events

AEs are to be monitored throughout the course of the clinical study from the time the informed consent form has been signed. All AEs are to be reported on the AE form of the eCRF with complete information as required.

If AEs occur, the main concern shall be the safety of the subjects. At the time of the ICF signature, each subject must be provided with the name and phone number of clinical study center personnel for reporting AEs and medical emergencies.

7.2.6.1 Definitions

7.2.6.1.1 *Adverse Events (AE)*

According to ICH E2A, an AE is any untoward medical occurrence in a patient or a clinical investigation subject administered a pharmaceutical product and which does not necessarily have a causal relationship with this treatment. An AE can therefore be any unfavorable and unintended sign (including an abnormal laboratory finding), symptom, or disease temporally associated with the use of a medicinal (investigational) product, whether or not related to the medicinal (investigational) product.

Thus any new sign, symptom or disease, or any clinically significant worsening of an existing sign, symptom or disease (including new episodes of a chronic disease [e.g., hay fever, allergy]) compared to the condition at the first visit, should be considered as an AE. Lack of efficacy is not considered as an AE.

Notes:

- There should be an attempt to report a diagnosis rather than the signs, symptoms or abnormal laboratory values associated with the report of an AE. However, a diagnosis should be reported only if, in the investigator's judgment, it is relatively certain. Otherwise, symptoms, signs, or laboratory values should be used to describe the AE.
- Pregnancy is not to be considered as an AE; however, is an important medical event that must be monitored as described in Section 7.2.6.2.3.

7.2.6.1.2 *Treatment Emergent Adverse Event (TEAE)*

A TEAE is an event that emerges during treatment, having been absent pre-treatment, or worsens relative to the pretreatment state.

Investigators are responsible for monitoring, recording, and reporting all AEs that occur during the study as described. TEAEs will be delineated from AEs following database lock.

7.2.6.1.3 *Serious Adverse Events (SAE)*

A SAE is any untoward medical occurrence that at any dose:

- Results in death,
- Is life-threatening,
- Requires inpatient hospitalization or prolongation of existing hospitalization,

- Results in persistent or significant disability/incapacity, or
- Is a congenital anomaly/birth defect.

Important medical events that may not result in death, be life-threatening, or require hospitalization may be considered an SAE when, based upon appropriate medical judgment, they may jeopardize the safety of the subject, and may require medical or surgical intervention to prevent one of the outcomes listed in this definition. Examples of such events are intensive treatment in an emergency room or at home for allergic bronchospasm, blood dyscrasia, or convulsions that do not result in hospitalization.

Note: The term “life-threatening” refers to an event in which the subject was at risk of death at the time of the event; it does not refer to an event which hypothetically might have caused death if it were more severe.

Inpatient hospitalization is considered to have occurred if the subject has had to stay for a night at the hospital. The criterion for prolongation of hospitalization is also defined as an extra night at the hospital. Hospitalization may not constitute sufficient grounds to be considered as an SAE if it is solely for the purpose of a diagnostic test(s) (even if related to an AE), elective hospitalization for an intervention that was already planned before subject enrolment in the clinical study, admission to a day-care facility, social admission (e.g., if the subject has no place to sleep), or administrative admission (e.g., for a yearly examination).

7.2.6.1.4 *Unexpected Adverse Drug Reaction*

An unexpected adverse drug reaction is defined as an adverse reaction, the nature or severity of which is not consistent with the applicable study product information (e.g., Investigator’s Brochure for an unapproved investigational product or the medicinal package insert/summary of product characteristics for an approved investigational product).

7.2.6.1.5 *Adverse Event Reporting Period*

The clinical study period during which AEs must be reported is the period from when the subject signed the ICF to the end of the subject’s participation.

The Sponsor should be informed if the Investigator becomes aware of any unusual safety information or any safety information that appears to be drug-related involving a subject who has participated in a clinical study, even after a subject has completed the clinical study.

7.2.6.1.6 *Severity*

Severity is a clinical determination of the intensity of an AE and not the severity of a disease.

The Investigator is to classify the intensity of AEs using the following definitions as a guideline. For this classification, the Investigator will take into account the possible range of the intensity of the event and report the grade of intensity which is the most appropriate according to his/her medical judgment.

Mild	Awareness of signs or symptom, but easily tolerated.
Moderate	Discomfort, enough to cause interference with usual activity.
Severe	Incapacitating with inability to work or perform usual activity.

